#### Intervention Period:

During the intervention period, subjects will receive in-office sessions of acoustic stimulation linked to brainwave activity (HIRREM, HCC), while relaxing in a zero gravity chair. Sessions last about 1.5-2 hours, and two can be done in a half day, with a short break between sessions. All subjects must receive the initial 6 sessions, two per day, on three consecutive days. Thereafter, subjects are encouraged to get the complete all sessions within two to three weeks, and in no longer than 4 weeks, without going longer than 5 days between sessions. Those assigned to the CCC group will continue with their current clinical care, including any life-style, non-pharmacological therapies that they may be employing.

#### Post-Intervention Data Collection Visits:

For participants in the HCC group, participants will return for a post-intervention data collection visit (V2, primary outcome) between 4-6 weeks after completion of the intervention. This will occur at 10-12 weeks after V1 for those in the CCC group. All measures will be repeated, including a brainwave assessment. This visit will require about 120 minutes.

Between 12-14 weeks after completion of the intervention, participants in the HCC group will return for a final data collection visit (V3). The V3 visit will be between 18-20 weeks after V1 for those in the CCC group. All measures other than the brainwave assessment will be repeated for a final time. This will complete the official study involvement for participants in the HCC group, while those in the CCC group will be offered an opportunity to be scheduled to receive a course of HCC, and this will be discussed. This visit will take about 45 minutes.

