### Overview:

[figure not shown]
This will be a randomized, single site, pilot clinical trial. Assuming a potential drop-out rate of 20%, up to 48 subjects will be enrolled to achieve a goal of having at least 40 subjects (20 per group) complete the study, per protocol. Patients who have at least 5 hot flashes per day (with at least one being categorized as moderate to severe) will be eligible to participate.

Those who have no other exclusions, are interested to participate, and provide informed consent will be randomly assigned to receive 8-16 sessions of in-office acoustic stimulation linked to brainwave activity (HCC), over a maximum of 4 weeks, while continuing their other current clinical care, or to continue their current clinical care alone (CCC). There will be pre- and post-intervention data collection to include a daily hot flash diary (to be completed for 7-14 days by both groups) and many secondary outcome measures including completion of the MRS, HFRDIS, measures of autonomic cardiovascular regulation (continuous recording of BP and HR for calculation of measure of HRV and BRS), behavioral symptom outcomes (ISI, PSQI, ESS, CES-D, GAD-7, PSS), quality of life measure (QOLS), and function performance measures (drop stick reaction testing, and grip strength). All measures will be collected at an enrollment visit (V1). Both groups will then maintain a hot flash diary for 7-14 days, after which the intervention will begin for the HCC group. Post-intervention data collections will include an intermediate post-intervention visit (V2, primary outcome, 4-6 weeks after intervention completion for HCC, and 10-12 weeks after V1 for CCC), and a final follow up visit (V3, 12-14 weeks following completion of the intervention for HCC, and 18-20 weeks after V1 for CCC). Both groups will maintain a hot flash diary for 1-2 weeks prior to the V2 and V3 visits. The primary outcome will be reduction in frequency and severity of hot flashes score from V1 to V2. Following V3, those in the CCC group will be offered the opportunity to receive a course of HCC within 3 months (will have another brainwave assessment 0-14 days before beginning sessions), and will continue to be followed for data collections at 4-6 weeks (V4), and 12-14 weeks (V5) after completing their HIRREM sessions.

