#### Number of Subjects:

As a pilot study, in a new cohort of participants, using a wait-list control, we are not able to calculate an accurate sample size. In order to evaluate feasibility and effect size, and allowing for up to 20% drop outs, we will arbitrarily enroll up to 48 subjects to achieve a goal of having 40 subjects complete the study per protocol (estimated 20 per group).

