The in-office HIRREM process is individualized for each recipient, such that the specific protocols chosen, the session length, and the total number of sessions are variable. Technologists time sessions and choose protocols to facilitate an overall trend toward greater hemispheric symmetry and more optimal proportionation in frequency ranges, between and within cortical regions, based upon data from the initial assessment and the ensuing sessions (Gerdes et al., 2013). Each participant in the HCC group will receive at least 8 sessions. The final number of HIRREM sessions, which may be extended to as many as 16, will depend on continuous review of brain patterns relative to progress towards improved balance and quieting of electrical amplitudes, as well as progress and stability of self-reported status regarding symptoms such as sleep and stress.

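### Follow-up visits in the HIRREM arm are timed only from an undefined completion of the course, so women who never start or stop before 8 sessions have no scheduled primary-endpoint visit, while every waitlist woman has one

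*Combined protocol and SAP*

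**What the plan says.** The section Post-Intervention Data Collection Visits sets different clocks for the two arms.

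- **HCC, V2:** "participants will return for a post-intervention data collection visit (V2, primary outcome) between 4-6 weeks after completion of the intervention".
- **CCC, V2:** "This will occur at 10-12 weeks after V1 for those in the CCC group".
- **HCC, V3:** "Between 12-14 weeks after completion of the intervention, participants in the HCC group will return for a final data collection visit (V3").
- **CCC, V3:** "The V3 visit will be between 18-20 weeks after V1 for those in the CCC group".

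The abstract's Methods, the Overview and the section on number of sessions and length of study use the same clocks. The Overview, for example, gives "V2, primary outcome, 4-6 weeks after intervention completion for HCC, and 10-12 weeks after V1 for CCC".

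Under Menopause-related symptoms, the first diary follows V1 in both arms, and later diaries fill the 7 to 14 days ahead of each later visit. The primary endpoint therefore depends on the visit date.

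Completion of the intervention is not defined. The nearest statements concern delivery. HIRREM Sessions says "Each participant in the HCC group will receive at least 8 sessions" and allows up to 16, depending on progress. Intervention Period says "All subjects must receive the initial 6 sessions, two per day, on three consecutive days" and sets an outer limit of 4 weeks.

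The aim in Number of Subjects is to "achieve a goal of having 40 subjects complete the study per protocol". Participant Compensation is the only section that mentions women who do not finish the study, and it deals with prorated payment. Statistical Analysis names no analysis population and no rule for missing data.

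**The concern.** A visit timed from an event has no date for a woman in whom the event does not occur. In HCC this affects the woman who never starts after her first diary and the woman who stops before 8 sessions. No CCC woman can lose her visit this way, because everyone has a V1 date.

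Stopping is unlikely to be unrelated to outcome. The trial is open-label, and a woman may stop because she feels no benefit, has unwanted effects or has worsening symptoms. If such women are not seen, the V1-to-V2 contrast sets HCC women who finished against CCC women without a matching selection, and HIRREM would tend to look better than it is.

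A mixed model would not recover the loss. No diary is scheduled during the session period, so an unseen stopper contributes baseline diary data only. The model would have no record of the early response that may have led her to stop. This matters because the trial's stated purpose includes supplying effect sizes that might justify larger trials.

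**Working it through.** **1. The plan's own enrolment figure.** Inputs from Overview and Number of Subjects: 40 completers, 20% drop-out, up to 48 enrolled. (The abstract gives up to 40 enrolled; 48 is used here.)

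- 40 × 1.20 = 48, which reproduces the plan's figure.
- 40 / (1 − 0.20) = 50 would be needed for a true 20% loss, and 48 × 0.80 = 38.4.
- The loss implied by going from 48 to 40 is 8/48 = 16.7%. With 24 per arm and 20 expected to complete, that is 4 of 24 in each arm.

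**2. Who has no visit date.**

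| Participant | Event that starts the clock | V2 date defined? |
|---|---|---|
| Any CCC woman | V1 | Yes |
| HCC, 8-16 sessions | Completion (can be read as the last session) | Yes, on a reasonable reading |
| HCC, 1-7 sessions | Not stated | No |
| HCC, never started | None | No |

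**3. Whether the protocol already contains a usable window.** Inputs: sessions begin 7-14 days after V1; the course lasts at most 4 weeks.

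- Latest end of course: 2 + 4 = week 6 after V1.
- V2: 6 + (4 to 6) = weeks 10-12. V3: 6 + (12 to 14) = weeks 18-20.

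These equal the CCC windows, so no new timing has to be invented. They also lie within the range possible for completers. With a start on day 7 and 8 sessions in 4 days, V2 can fall as early as (7 + 3)/7 + 4 = 5.4 weeks after V1; the latest is 12.0 weeks.

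**4. Illustrative size if stoppers are not seen.** Let *p* be the share of HCC women who stop early, *Dc* the mean change in completers and *Ds* that in stoppers. The all-randomised HCC mean is (1 − *p*)*Dc* + *pDs*, so the completer-only mean differs from it by *p*(*Dc* − *Ds*). If *Ds* = 0, the relative overstatement is 1/(1 − *p*) − 1. If *Ds* = *Dc*/2, it is 1/(1 − *p*/2) − 1. The documents give neither *p* nor *Ds*; both are assumed. The last column assumes stoppers do 0.5 to 1.0 SD worse than completers.

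| HCC stoppers of 24 | *p* | Overstated if *Ds* = 0 | Overstated if *Ds* = *Dc*/2 | Shift in HCC mean |
|---|---|---|---|---|
| 2 | 8.3% | 24/22 − 1 = 9% | 24/23 − 1 = 4% | 0.04-0.08 SD |
| 4 (plan's implied loss) | 16.7% | 24/20 − 1 = 20% | 24/22 − 1 = 9% | 0.08-0.17 SD |
| 8 (all of the trial's loss in HCC) | 33.3% | 24/16 − 1 = 50% | 24/20 − 1 = 20% | 0.17-0.33 SD |

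The percentages refer to the HCC change, not to the difference between arms. The same absolute amount enters the between-arm contrast if CCC losses are unrelated to outcome.

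**5. Power.** For an assumed effect of 0.8 SD at two-sided 0.05 (normal approximation), power is 0.72 with 20 against 20 and 0.70 with 16 against 24. The issue is bias, not power.

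**The case against.** The strongest reply is that the protocol is silent on stoppers and does not exclude them. Nothing withdraws a woman who stops sessions. Other Data Collection, Measures, and Process describes post-intervention measures for all participants, the diary instruction is not limited to completers, and compensation is paid per data-collection visit and for diaries, never per session. Staff could count from the last session or from the end of the 4-week limit.

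Most of this stands, and it limits the point. A reader might infer that HCC stoppers are necessarily lost; the documents do not say so. A reader might also combine the 8-session minimum, the consecutive-day start, the 5-day gap and the 4-week limit into one test of completion. Those are delivery instructions, the gap sits in a sentence of encouragement, and a woman who stops at 8 to 15 sessions may well count as complete. First-diary data are unaffected in either arm.

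The gap remains. The reference to all participants carries no timing, and it counts three post-intervention visits where the schedule has two. Counting from the last session would be improvised and gives a never-starter no date. A target stated in per-protocol completers gives staff no reason to pursue these women.

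**Conclusion.** The concern holds as a risk created by the wording. For HCC women who never start or stop before 8 sessions, the protocol schedules no V2, V3 or pre-visit diary and does not say that they are followed. Data not collected at V2 cannot be recovered at analysis.

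The direction is likely to favour HIRREM, on the assumption that stoppers do worse than completers. If women stopped because they felt better, it would reverse.

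The size is unknown. The 20% figure rests on all 4 implied HCC losses being early stoppers, no change in any of them, and none being seen at V2. Ordinary loss to follow-up and stopping after 8 or more sessions do not arise from the timing rule. A reader might apply the stated 20% drop-out to HCC and get 1/0.80 − 1 = 25%; the plan's own numbers give 16.7%, and nothing says that all drop-out is early stopping. The pilot's change in hot flash frequency should not be used to put this in flashes per day: it is a median, to the final day of sessions, in 12 women without a control group.

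**What to change.** 1. State that stopping sessions is not withdrawal from follow-up, and define completion for the purpose of visit timing.
2. See every randomised HCC woman at V2 and V3, with the same 7-14 day diaries beforehand. Where there is no completion date, use the windows already set for CCC: 10-12 and 18-20 weeks after V1.
3. Run the primary V1-to-V2 hot flash contrast in all randomised women with diary data, by assigned arm, and keep a defined per-protocol set as supportive. Statistical Analysis must be amended for this in any case, since it currently names blood pressure from V1 to V3 as the primary test.
4. Record the number of sessions received and the reason for stopping.

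No rule on delivering treatment changes. The cost is protocol wording and some extra effort to retain women who stop, for visits and diaries already planned for each participant. The estimated effect may be smaller, but it would describe everyone assigned to HIRREM.

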#### High-resolution, relational, resonance-based, electroencephalic mirroring (HIRREM):

High-resolution, relational, resonance-based, electroencephalic mirroring (HIRREM®) is a computer-based technology created by Brain State Technologies, LLC, Scottsdale, AZ, designed to facilitate relaxation and auto-calibration of neural oscillations through reflecting back musical tones in near real time.

### Brainwave Assessment:

This is the first step in the HIRREM process. It occurs during the V1 enrollment visit, and will be performed on both groups. The assessment creates a map of frequencies and amplitudes, and informs the choice of protocols for the initial HIRREM sessions. Our pilot data also suggest that this information is also useful for correlating with autonomic function (HRV and BRS), and that changes can be observed in frequencies and amplitudes from pre- to post-HIRREM. For the assessment, with the participant in a sitting position, sensors are sequentially placed over six areas of the scalp to record one minute epochs of data while the brain is at rest, or on task, with eyes open and with eyes closed. For the assessment, measurements are taken at homologous regions of the bilateral hemispheres according to the 10-20 International System at F3/F4, C3/C4, P3/P4, T3/T4, FZ/OZ, O1/O2, FP1/FP2, and CB1/CB2 with both eyes closed (EC; one minute), and eyes open (EO; one minute) conditions ("Report of the committee on methods of clinical examination in electroencephalography: 1957," 1958). For EO assessments, subjects are given standardized tasks involving numerical digit recall (F3/F4), reading silently (C3/C4), math calculations (P3/P4), listening comprehension (T3/T4), and to relax with eyes open (O1/O2). A sixth midline measurement is taken at FZ/OZ, with an EO task to count number of appearances of a specific word as they read a standardized printed passage. A seventh (FP1/FP2, given standardized tasks involving numerical digit recall), and eighth (CB1/CB2, relax with eyes open) location are also measured. The reference sensors are connected at A1/A2 and linked for assessments. The data are processed to identify patterns and imbalances of frequencies and amplitudes, which are used to generate specific protocols for the initial HIRREM session. The assessment takes about 30-45 minutes to complete. An assessment will be repeated at the V2 visit to allow comparison between brain patterns at baseline, and post-intervention, between the two groups.

### HIRREM Sessions:

Participants assigned to both study groups will continue their current clinical care. The HIRREM intervention group (HCC), will also receive a course of 8-16 in-office HIRREM sessions. Each session requires about 1.5-2 hours, and will include between 3-10 individual protocols, working with different locations on the scalp. Each protocol will typically last from 6-40 minutes. For the sessions, with the subject comfortably at rest, sitting or reclining, the sensors are placed over the specific target areas on the scalp corresponding with brain regions/lobes to be observed. Brainwaves are monitored in real time, and the dominant frequency within a chosen target frequency band, e.g. delta (0.5-3 Hz) is identified. The dominant frequency is assigned an auditory tone which is played back to the subject via ear phones with as little as 4-8 millisecond second delay. Thus, the subject listens to the energetic "song" being played in the brain from moment to moment, providing the brain with rapid updating about its frequencies, amplitudes, and patterns via an electronic/acoustic mirror of itself.

Some sessions will occur with eyes closed, for which the subject will be instructed to relax. Some sessions will occur with eyes open, during which the subject can read, or do other activities such as a word search, or just relax.

Although there are similarities to methods such as neurofeedback, or traditional biofeedback, HIRREM uses an algorithm-based observation for the brain to view itself, which provides an opportunity for subject-unique auto-calibration, self-adjustment, and movement towards a more balanced state, rather than operant conditioning designed to try to force the brain toward a standardized or ideal pattern of frequencies and amplitudes. In addition, no active, conscious, cognitive involvement by the participant is needed to accomplish this process.

The in-office HIRREM process is individualized for each recipient, such that the specific protocols chosen, the session length, and the total number of sessions are variable. Technologists time sessions and choose protocols to facilitate an overall trend toward greater hemispheric symmetry and more optimal proportionation in frequency ranges, between and within cortical regions, based upon data from the initial assessment and the ensuing sessions (Gerdes et al., 2013). Each participant in the HCC group will receive at least 8 sessions. The final number of HIRREM sessions, which may be extended to as many as 16, will depend on continuous review of brain patterns relative to progress towards improved balance and quieting of electrical amplitudes, as well as progress and stability of self-reported status regarding symptoms such as sleep and stress.

#### Safety:

Evidence to date indicates that the HIRREM intervention has potentially high benefit and low risk. Based on experience reported by Brain State Technologies, garnered from provision of case management support, feedback from their clients, and feedback from the HIRREM provider community, as well as results from IRB-approved studies at WFSM (now over 480 participants to receive HIRREM), we are not aware of any serious adverse events resulting from HIRREM sessions.

Non-serious, temporary, effects have been reported by participants in other studies. This includes things such as the participant reporting being more aware of, or more affected by their feelings, or by those around them, changes in sleep, including dreams, emotions, or energy levels, or a feeling of fullness in the head or mild headache. In the course of provision of HIRREM as part of five IRB-approved studies at WFSM, such non-serious, temporary effects have been estimated to occur in ten percent or less of participants. Based on recent analysis of a placebo controlled trial of HIRREM for moderate to severe insomnia (n = 107), such non-serious, temporary adverse effects that were judged to go beyond the intensity, expression, or nature of pre-existing health conditions were reported during study participation by 10.7% in the HIRREM group, and 13.7% in the placebo group. All episodes were brief, typically resolving in hours to 1-2 days, but at the most lasted less than one week. Skin irritation at the site from the paste used to affix the sensors to the scalp was reported by a single participant (<1%) (personal communication).

All HIRREM sessions are administered by Technologists who have been certified in the procedure, including guidelines for addressing any adverse effects that may occur. In the event that any adverse effect is prolonged or intense, participants will be advised to see their primary care physician, or if needed, to see a mental health professional for additional evaluation or treatment. It acute, and severe,

participants will be referred to the Emergency Department. There are no anticipated additional risks associated with continuation of current clinical care.

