Any collected patient identifying information corresponding to the unique study identifier will be maintained on a separate master log. The master log will be kept secure, with access limited to designated study personnel. Following data collection subject identifying information will be destroyed at the earliest opportunity, consistent with data validation and study design, producing an anonymous analytical data set. Data access will be limited to study staff. Data and records will be kept locked and secured, with any computer data password protected.

Reporting of Unanticipated Problems, Adverse Events, or Deviations:

Any unanticipated problems, serious and unexpected adverse events, deviations or protocol changes will be promptly reported by the principal investigator or designated member of the research team to the IRB and sponsor or appropriate government agency if necessary.

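### The plan describes no item for recording the brief non-serious effects it expects, and incidental reports would come from one group only, so it cannot support a between-group tolerability statement

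*Combined protocol and SAP*

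**What the plan says.** The Safety section lists the non-serious effects reported in other HIRREM studies. It adds that "such non-serious, temporary effects have been estimated to occur in ten percent or less of participants". For an earlier placebo-controlled insomnia trial of 107 participants it states that such effects were "reported during study participation by 10.7% in the HIRREM group, and 13.7% in the placebo group". On duration it says: "All episodes were brief, typically resolving in hours to 1-2 days, but at the most lasted less than one week".

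On collection and reporting:

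- **Reporting of Unanticipated Problems, Adverse Events, or Deviations:** "Any unanticipated problems, serious and unexpected adverse events, deviations or protocol changes will be promptly reported".
- **Data and Safety Monitoring:** the principal investigator is responsible for safety monitoring, with help from study staff. No data to be monitored are named.
- **Safety:** technologists are certified and have guidance on handling adverse effects, with a referral route. No duty to record is stated.
- **Post-Intervention Data Collection Visits:** HCC women return for a "post-intervention data collection visit (V2, primary outcome) between 4-6 weeks after completion of the intervention". CCC women return 10-12 weeks after V1.
- **Menopause-related symptoms:** the diary covers hot flash frequency and severity, for 7-14 days after V1 and 7-14 days before each later visit.

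**The concern.** Effects that last hours or days must be asked about close to when they happen. If they are not, they cannot be recovered later. The plan names the effects it expects but describes no way of collecting them. The only chance of hearing about them is at HIRREM sessions, which CCC women do not attend.

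The pilot is meant to inform larger trials (Abstract, Importance), and the Background presents safety worries about hormone therapy as the reason to seek alternatives. A tolerability table collected alike in both groups would be a natural product of such a pilot. Followed as written, the plan gives either no such table or one whose two columns were gathered differently.

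**Working it through.** **1. The plan's own figures.** The rates "10.7% in the HIRREM group, and 13.7% in the placebo group" with a total of 107 were checked against all whole-number counts with arm sizes from 40 to 67. One solution fits: 6/56 = 10.7% and 7/51 = 13.7%, with 56 + 51 = 107. The single skin-irritation report is 1/107 = 0.93%, in line with the stated figure of under 1%. Fisher's exact test on 6/56 against 7/51 gives p = 0.77. In that trial, placebo sessions produced such reports about as often as HIRREM sessions, so a count from treated women alone says little about the treatment.

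**2. Where an item could be.**

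| Section | Adverse-effect item or summary described? |
|---|---|
| Secondary Objectives; Overview | No |
| Measures, from Demographics to Grip Strength | No |
| Appendix A, list of forms | No |
| Statistical Analysis | No safety summary |
| Reporting of Unanticipated Problems, Adverse Events, or Deviations | Prompt reporting of unanticipated problems, serious and unexpected events, deviations and protocol changes; not expected, non-serious effects |

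The sleep, mood, anxiety and stress scales overlap with some of the named effects. They are outcome scales taken at visits, and they do not record the onset or duration of an episode, or head and skin effects.

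**3. Contact between V1 and V2.**

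- HCC: 8-16 sessions, the first six on three consecutive days and then no more than 5 days apart (Intervention Period).
- CCC: V2 falls 70-84 days after V1. The stretch with neither diary nor visit runs from 70 - 14 - 14 = 42 days to 84 - 7 - 7 = 70 days.

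**4. The interval before V2 in HCC.** V2 is 28-42 days after the last session. An effect that starts at the last session and lasts under 7 days is over at least 28 - 7 = 21 days before V2. The pre-V2 diary opens 28 - 14 = 14 to 42 - 7 = 35 days after the last session, also after such an effect has ended. An effect that starts during the course could be noticed at a later session. The interval therefore matters only for effects arising at or after the last sessions.

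**5. Unequal time under observation.** Sessions start 7-14 days after V1. The shortest course is 4 days (six sessions on three days, then two on a fourth) and the longest is 28 days. V1 to V2 in HCC is therefore about 7 + 4 + 28 = 39 to 14 + 28 + 42 = 84 days, against 70-84 days in CCC.

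**6. What 20 per group could show.** The exact (Clopper-Pearson) 95% interval for 2/20 is 1.2% to 31.7%. For 0/20 the upper limit is 16.8%. Assuming a two-sided 5% test, power for 10.7% against 13.7% with 20 per group is about 5%, and 80% power would need about 1,868 per group.

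**The case against.** **HCC women are seen often.** They are seen by trained technologists, and self-reported status is reviewed throughout to decide the number of sessions (HIRREM Sessions). A reader might infer from the interval before V2 that brief effects would all be missed. The documents do not support that: most effects during the course could come to a technologist's notice. What stands is that no one is told to record them, and that CCC has no counterpart.

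**A predicted false excess is not shown.** A reader might apply 13.7% to CCC, expect about 24 x 0.137 = 3.3 affected women in a group of 24, and conclude that any HCC excess would be pure ascertainment. That rate comes from women receiving placebo sessions in an insomnia trial. CCC receives no sham sessions, and the Safety section anticipates no added risk from continued current care. CCC women also attend V2 and V3, so zero capture is not established. The one-sidedness is real, but its size cannot be derived from the documents.

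**The plan promises no adverse-effect rate.** No safety objective is stated, and the Background speaks of the need for safe therapies in general. The reporting rule governs what is sent on promptly, which need not define everything that is recorded. These points limit the weight of the concern.

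**Some material is unseen.** The flow chart, the contents of Appendices A-C and the technologists' guidance are not visible. An adverse-effect item there cannot be excluded.

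**Conclusion.** The concern holds for the non-serious effects named in the Safety section. On the available text, the plan specifies neither their recording nor their tabulation. Contact is frequent in HCC, while CCC has a 42-70 day stretch with neither diary nor visit, so any incidental record would be one-sided and could not support a between-group tolerability statement. The interval before V2 is a secondary contributor.

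This is worth correcting before enrolment because episodes not asked about near the time are lost. It does not touch the efficacy comparison or the handling of unanticipated problems and serious and unexpected events. It assumes that no item sits in the unseen material. It should not be read as showing that the trial will report a false excess with HIRREM. Nor would better collection make this pilot informative about small differences: at 20 per group the result remains descriptive.

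**What to change.** Add one short fixed checklist of the effects in the Safety section (yes/no, start, stop, intensity) with one open question. Both groups complete it themselves, with the same recall period:

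- at V1;
- with the post-V1 diary and the diaries before V2 and V3;
- at V2 and V3;
- once more at a matched time since V1, near the end of the HCC course. The latest course end is 14 + 28 = 42 days after V1.

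Record effects noted at HCC sessions too, but list them separately as not comparable with CCC. In Statistical Analysis, add counts and proportions by randomised group, with exact 95% confidence intervals and the length of the observation window, labelled descriptive. If an item already exists in the flow chart or appendices, cite it in the protocol text.

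While editing, reconcile the number of visits. The section on other data collection gives three post-intervention visits for all participants; the Overview and visit sections describe two (V2 and V3).

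The cost is one form, a slight participant burden, and higher counts from prompting in both groups. Weekly staff calls would be a poorer choice. They add staff work and alter the waitlist condition in a trial with a diary outcome, and the protocol describes phone and email contact only for recruitment.
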